Method: After their Well Check Visit with their pediatrician, adolescents will be recruited virtually or in-person to complete a screening survey about substance use. Participants who are ineligible to complete the study because they did not use substances or have friends that use substances in the past year will receive the recommended reinforcing message for abstaining from substance use such as “You’ve made a smart decision not to use alcohol or drugs” to reinforce choice (adapted from the Alcohol Screening and Brief Intervention for Youth⁶³). This “screening out” procedure will allow for adolescent substance non-use to be reinforced in the recommended manner to save time for providers by providing evidence-based care. Eligible participants (and their guardian) will be invited to meet with a research assistant either in person at the clinic, by phone, or in

a video conference meeting to discuss the research and obtain consent. While discussing informed consent, participants and their guardians will be informed of the sensitive nature of the prevention program and that the adolescent will complete the brief survey and then research procedures. Both the adolescent and guardian will be informed that if the adolescent discloses a SA history as a child that has not been previously reported to the appropriate officials (Department of Social Services or Law Enforcement depending on the perpetrator), a report will need to be made prior to the adolescent and guardian leaving the clinic. Both the adolescent and guardian will be informed that if the adolescent discloses imminent risk of suicide and the adolescent is not willing to agree to a safety plan, a mental health professional will need to conduct an exam to determine if hospitalization is needed.

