The two potential risks to participants that may be associated with involvement in the study include: 1) potential threats to confidentiality, particularly with regard to reporting sexual assault and reporting of imminent suicide risk without agreeing to a safety plan; and 2) potential embarrassment or distress from responding to questions or engaging in the prevention program targeting sensitive topics including substance use, sexual assault, and sexual risk behaviors. These risks are discussed in greater detail below. In addition, although not a risk specifically linked with participating in the study, the vulnerability of adolescents who have experienced sexual assault necessitate consideration of procedures in the cases of psychiatric emergencies (e.g., suicidal attempts). These considerations are noted here and in the following Protection Against Risk section.

First, regarding potential threats to confidentiality, there may be emotional and/or legal consequences if personal information obtained during the assessment is released to outside parties. That is, mandatory reporting laws necessitate that new disclosures (i.e., previously unreported) of qualifying incidents of child abuse (including SA of someone under the age of 18 years old), be reported to the Department of Social Services/DSS (when perpetrator of abuse is in a caretaking position) or the local law enforcement agency (when perpetrator of abuse is in a non-caretaking position). Reports to such agencies may result in DSS involvement with the family, removal of family members or child from the home, or criminal charges/arrests. With regard to likelihood of this threat to confidentiality in relation to child abuse reporting, sexual assault history will be initially assessed through the assessment during the feasibility trial prior to beginning the prevention program. Participants will be informed of these risks of mandatory reporting laws prior to completing the assessments. A research assistant and licensed psychologist (e.g., P.I. [name]) will be immediately informed if an adolescent discloses a sexual assault victimization.

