Further, if an adolescent indicates that they have suicidal ideation within the survey, this will prompt a full suicide risk assessment (see Safety Plan) to be completed by the research personnel supervised by a licensed mental health professional. If there is acute risk of suicide, the guardian will be informed. The safety plan—detailing what to do and whom to speak with if ideation should occur—will be discussed with all adolescents who screen positive for suicidality, including specifics on how to access 24-hour care for

suicidality via dialing 9-1-1 and/or going to the closest emergency department when a mental health professional is not available.

If there is any disclosure requiring reporting, the research personnel (supervised by a licensed mental health professional) will contact both the adolescent and guardian (if under 18, or adolescent alone if 18) to discuss mandated reporting and to provide any needed referrals for treatment. A report will be made to the appropriate location (DSS or law enforcement agency) by the researcher under the supervision of a licensed mental health professional.

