For participants enrolled in the study, in any circumstances where a research assistant or a licensed psychologist is concerned regarding suicidal ideation or attempt, the P.I. will be contacted immediately. All research staff will have a cell phone number where the P.I. will be available 24 hours 7 days a week. In rare instances where she cannot be reached, a licensed psychologist will serve as a back-up. [name] will ensure research assistants are well-trained in assessing distress and suicidality (intent, plan, etc) using a Safety Plan that includes the Linehan risk assessment and management protocol (LRAMP) (see "TWC Suicide Safety Plan Revised 041321"). In circumstances where adolescents in either condition express suicidal ideation and are sincerely willing to contract for safety (i.e., will agree to keep her/himself safe), the guardian will not be informed. The safety plan—detailing what to do and whom to speak with if ideation should occur—will be discussed with all participating adolescents who screen positive for suicidality, including specifics on how to access 24-hour care for suicidality via dialing 9- 1-1 and/or going to the closest emergency department (research staff will help families determine this location) when a licensed psychologist and/or supervisor is not available. Thus, a 24-hour safety plan is in place, including access to medical care 24 hours per day. Further, any participant in which it is deemed that medication is warranted will be referred to a hospital or community-based psychiatrist for such services and monitoring. Suicidal risk factors - including suicidal ideation, intent, plan, and means - will continue to be assessed on an ongoing basis throughout the adolescents' participation in the study via the baseline and follow-up surveys.

If a participant is deemed at risk for suicide and the adolescent will not contract for safety, or has made any indication of acute suicidal risk, the guardian will be informed immediately and the adolescent will be assessed by local emergency department for possible inpatient hospitalization.

In all surveys, if a teen reports a sexual assault or suicidal ideation while completing the online survey, a notification will be made to [name] automatically. No matter the teen's responses, all teens will receive information for the suicide hotline and information about how to report a sexual assault if they have experienced one as a child. However,

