For participants enrolled in the study, in any circumstances where the study staff is concerned regarding suicidal or homicidal ideation or attempt, or SA perpetration against a minor, s/he will immediately contact [name], who is a licensed psychologist in South Carolina (License No. PSY.1417). [name] will assess safety and provide instructions to the study staff to address any risks. [name] will ensure that the study staff are well-trained in assessing distress and suicidality (ideation, intent, plan, etc). In circumstances where participants express suicidal ideation and are sincerely willing to contract for safety (i.e., will agree to keep her/himself safe), a plan will be made and carefully monitored. If a participant is deemed at-risk for suicide and will not contract for safety or has made a suicidal behavior or attempt, the participant will be assessed by a local emergency department for possible inpatient hospitalization. [name] or trained research staff will also ensure that participants who present with risk for suicidal or homicidal ideation are well educated on how to access 24-hour emergency care (through 9-1-1 or going to the local Emergency Department). [name] will be on-call for study therapists, 24 hours per day, 7 days per week.

B. Procedures for Monitoring Safety of Data

Regarding data management and storage, all data will be collected using computerized self-report questionnaires. Only participants' study identification codes will be inputted computer-based databases. The codes that link the name of the participant and the study ID will be kept confidential by [name] in a secured cabinet. The data will be imported directly into a password-protected SPSS data file stored on the GSU server. The server is protected by the GSU network, and a secured log-in is required from all users. All research personnel collecting and manipulating data will have completed a Human Subjects Research Training and will meet weekly with [name] or a postdoctoral fellow in the lab to ensure strict compliance with the DSM plan. Only study personnel (candidate, research staff, and mentorship team) will have access to data. No data will be released to other agencies unless participants consent to release.

Adverse Events

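### The protocol states three different triggers for emergency or hospitalization assessment of a suicidal adolescent, and leaves guardian notice unclear when one at acute risk agrees to a safety plan

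*Combined protocol and SAP*

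**What the plan says.** Three sections state when a suicidal adolescent goes for emergency or hospitalization assessment.

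- **Section 4-2.A (Method)**, describing the consent discussion, sets this condition: "if the adolescent discloses imminent risk of suicide and the adolescent is not willing to agree to a safety plan". The stated consequence is an examination, by a mental health professional, of the need for hospital admission. Section 6 (Potential Risks/Discomforts) describes the confidentiality risk in the same joint form: "reporting of imminent suicide risk without agreeing to a safety plan".
- **Section 6 (Protection Against Risks)**: for a participant judged at risk, if "the adolescent will not contract for safety, or has made any indication of acute suicidal risk, the guardian will be informed immediately", with assessment at a local emergency department as the second step.
- **Section 12.A (Participant Safety)**: "If a participant is deemed at-risk for suicide and will not contract for safety or has made a suicidal behavior or attempt", emergency department assessment follows. A participant with ideation who contracts for safety gets a monitored plan.

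Rules on telling the guardian appear only in Section 6. Potential Risks/Discomforts says: "If there is acute risk of suicide, the guardian will be informed". Protection Against Risks says that where adolescents "express suicidal ideation and are sincerely willing to contract for safety (i.e., will agree to keep her/himself safe), the guardian will not be informed". Its next paragraph contains the immediate-notice sentence quoted above.

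Section 5.E provides for 18-year-olds to consent without a guardian. For mandated reports, Section 6 distinguishes participants under 18 from those aged 18.

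**The concern.** The three assessment rules are built differently. One joins its two conditions with *and*. The other two use *or*, but with different second branches: acute risk in one, behavior or attempt in the other. They cannot all select the same adolescents.

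Two things are at stake. The first is safety conduct. The participants are 14 to 18 years old, and Section 12.A itself treats suicidal ideation and attempts as possible in this population. A staff member working from Section 12.A would find a different instruction from one working from Section 6. The second is consent. Families told that imminent risk and refusal of a plan are both needed could face emergency assessment and guardian notice after the adolescent has agreed to a plan.

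**Working it through.** There is no figure in the plan to reproduce, so the check is a comparison of the rules.

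**Terms.** For an adolescent already judged at risk, let R = acute or imminent risk, N = will not agree to a safety plan or contract for safety, and B = a suicidal behavior or attempt. Two assumptions are needed because the protocol neither defines nor links these words. Imminent and acute are treated as the same level, and agreeing to a safety plan is treated as the same as contracting for safety.

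**Assessment triggers as written.**

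- Section 4-2.A: R and N
- Section 6, Protection Against Risks: N or R
- Section 12.A: N or B

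**Applied to the four cases without a behavior or attempt (B absent):**

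| Adolescent judged at risk | Section 4-2.A | Section 6 | Section 12.A |
|---|---|---|---|
| Not acute, agrees to plan | not met | not met | not met |
| Not acute, refuses plan | not met | met | met |
| Acute, agrees to plan | not met | met | not met |
| Acute, refuses plan | met | met | met |

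Not met means that the stated condition is not satisfied. It does not mean that assessment is forbidden.

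The rules agree in the first and last rows. The third row is the important one, because only Section 6 triggers there. It is also the only row in which Sections 6 and 12.A differ. Section 4-2.A is narrower than Section 6 in the second and third rows.

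**Guardian notice in the third-row case (acute risk, plan agreed, no attempt).**

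- Section 6, Potential Risks/Discomforts, acute-risk sentence: guardian informed.
- Section 6, Protection Against Risks, acute-risk sentence: guardian informed immediately.
- Section 6, Protection Against Risks, contract sentence: guardian not informed, if an adolescent at acute risk who contracts counts as one with ideation who contracts. The sentence makes no exception for acute risk.
- Section 6, Potential Risks/Discomforts, description of the confidentiality risk: the joint condition is not met.
- Sections 4-2.A and 12.A: no guardian rule.

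**18-year-olds.** None of these guardian sentences separates participants who consent alone. The age distinction made for mandated reports is not repeated for suicide risk.

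**How often.** Section 6 assesses suicide risk in the baseline and follow-up surveys: baseline, 1, 3 and 6 months, so 1 + 3 = 4 points per participant. That is the schedule, not an expected count. The documents give no rate of acute risk.

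**The case against.** The case on the other side is substantial.

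- **The two guardian sentences in Protection Against Risks can be read as graded.** The first covers ideation with a contract. The second moves up to refusal or acute risk, and its *or* reaches the adolescent who contracts but is at acute risk. The acute-risk sentence in Potential Risks/Discomforts points the same way. This is a sensible reading, but the text does not state the precedence, and the reading does not explain the different triggers in Sections 4-2.A and 12.A.
- **Neither of those two sections says *only if*.** A reader might infer that an adolescent at acute risk who agrees to a plan goes unexamined. The documents do not support that. Section 6 requires a full suicide risk assessment after any ideation reported in a survey. Section 12.A has participants who indicate any risk of harm assessed immediately, and has staff contact the lead psychologist, who assesses safety and gives instructions.
- **Silence is not contradiction.** A reader might also infer that three sections set rival guardian rules, or that the same adolescent is handled in opposite ways. Sections 4-2.A and 12.A set no guardian rule, and both acute-risk sentences in Section 6 inform the guardian.
- **Another document may settle the matter.** Section 6 cites a separate suicide Safety Plan, which may define the terms and rank the rules. It is not among the documents available, and neither are the consent forms. If it does settle the order, the protocol's own sections still need to match it.
- **An on-call psychologist decides.** Round-the-clock expert cover lowers the practical risk of inconsistent handling. It does not correct what families are told at consent.

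These points limit the concern to mismatched triggers and unstated precedence. They do not remove it.

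**Conclusion.** The point stands as an inconsistency in the safety and consent text, which is wrong as written. The emergency-assessment trigger takes three different forms, and a foreseeable case satisfies only one of them. The consent description is narrower than the rule in Protection Against Risks, and Section 12.A does not match that rule. On guardian notice the defect is smaller: precedence is unstated within Section 6, and the position of 18-year-olds is not given.

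The conclusion rests on treating imminent and acute risk as one level. If they were meant as different levels, the rules would still differ, and the protocol would need to define both. No number of affected participants can be given. No view is taken here on which clinical rule is right.

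**What to change.** Reconcile Section 4-2.A, both parts of Section 6 and Section 12.A to one stated trigger for emergency assessment and one for guardian notification. The text should:

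- define the risk terms it uses and use them consistently;
- state what happens when an adolescent at acute risk agrees to a plan;
- state which guardian sentence takes precedence;
- state how the guardian rule applies to 18-year-olds.

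Align the consent description and the Safety Plan with that text. The sponsor's clinical and IRB leads decide the content of the rule. The cost is wording in the protocol, consent material and Safety Plan, with one IRB amendment. Sample size, surveys and analysis are unaffected.

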[name] will be responsible for monitoring the safety and efficacy of this trial, executing the NIDA- approved Data and Safety Monitoring (DSM) plan, and complying with the reporting requirements. [name] will provide a summary of the DSM report to NIDA on an annual basis as part of the progress report. The DSM report will include the participants' socio-demographic characteristics, expected versus actual recruitment rates, any quality assurance or regulatory issues that occurred during the past year, summary of adverse events, and any actions or changes with respect to the protocol. The DSM report to NIDA will also include, when available, the results of any data analyses.

A. Participant Safety

Diligent safety monitoring will be conducted by the candidate throughout this study in compliance with the following required elements of the GSU IRB and continuing review process:

1. tracking of subject accrual (enrollment, drop-outs, demographics)
2. timely and appropriate reporting of informed consent process deficiencies, protocol deviations, privacy breaches, conflicts of interest, and/or changes in personnel
3. ongoing monitoring and appropriate reporting of adverse event activity: a. Internal: i) frequency of unexpected, related or possibly related, and serious or more prevalent than expected adverse events; ii) frequency of internal deaths occurring during the study or within 30 days of study termination, even if expected or unrelated b. External: frequency of unexpected, related or possibly related, and serious adverse events
4. interim assessment of risk/benefit relationship in reference to adverse event occurrences, preliminary observations, and emerging information
5. timely and appropriate IRB submission of safety-related documents such as audit reports, sponsor progress reports, and other materials or communications that might impact the safe conduct of this study
6. active cooperation with the IRB and other applicable entities in the event of a random or for-cause internal or external audit

Participant Safety Relevant to Specific Application. Regarding the risk of harm to self or others, the nature of the population (adolescents at risk for using substances, SA, and SRBs) entail that specific adverse events, such as suicidal and homicidal ideation and

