attempts, are possible given the high-risk nature of the population under study. Regardless, both expected adverse events and unexpected adverse events will be monitored and addressed continuously throughout the course of the project. Risk of harm to self and others will be directly assessed through self-report questionnaires. Participants in the study who indicate any risk of harm will immediately be assessed and referred for treatment, if needed. [name] and her mentorship team have extensive training in crisis management. [name] was directly clinically trained by [name], the developer of Dialectical Behavior Therapy which is effective at reducing suicidal behavior. Therefore, she is well versed and very experienced in the assessment and management of acutely suicidal individuals. Both expected and unanticipated adverse events will also be continuously monitored by the candidate and mentorship team. All study staff will be closely supervised by the candidate, who will hold weekly meetings with the staff to address clinical barriers, prevention program and enrollment progress, and safety issues throughout the feasibility trial. [name] will also be available 24/7 to study staff by phone if any additional support is needed. Participant safety is assessed routinely as part of the research context through assessments given at each time point to evaluate substance use, SA, SRBs, and risk of harm.

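### The automatic survey alert names sexual assault and suicidal ideation but not homicidal ideation or other non-sexual threats to others, for which the plan promises immediate assessment

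*Combined protocol and SAP*

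**What the plan says.** Section 6 (Protection Against Risks) describes an automatic alert that applies in all surveys: "if a teen reports a sexual assault or suicidal ideation while completing the online survey, a notification will be made to" a named individual. The text goes on to say that a supervised team member contacts the participant within 24 hours.

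Earlier in section 6, both listed risks also have their own link from disclosure to action. For sexual assault, a research assistant and a licensed psychologist "will be immediately informed if an adolescent discloses a sexual assault victimization". For suicide risk, "if an adolescent indicates that they have suicidal ideation within the survey, this will prompt a full suicide risk assessment".

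Section 12.A (Participant Safety) covers more than these two risks. It regards "specific adverse events, such as suicidal and homicidal ideation" and attempts as possible in this population. It states: "Risk of harm to self and others will be directly assessed through self-report questionnaires". It promises: "Participants in the study who indicate any risk of harm will immediately be assessed and referred for treatment, if needed". It adds that safety is assessed routinely "through assessments given at each time point to evaluate substance use, SA, SRBs, and risk of harm". It then sets out an escalation to the study psychologist in circumstances "where the study staff is concerned regarding suicidal or homicidal ideation or attempt", or where staff are concerned about sexual assault perpetration against a minor.

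Section 5.B has every participant complete the 1-, 3- and 6-month surveys online, in a private place of their own choosing. Baseline may also be done remotely.

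**The concern.** For a harm-to-others answer, the plan states the duty (assess), the trigger (the participant's own answer) and the timing (at once). It does not state how the answer gets from the survey to a person who can act. For the other two survey-reported risks that link is written down.

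The omission matters because of remote completion. In a clinic a research assistant might notice distress or be told something. At follow-up no staff member need be present, so the automatic alert is the only written mechanism that works in real time. If the survey is programmed to the rule as stated, an answer indicating homicidal ideation or a threat to someone else would raise no notification. The immediate assessment could then be missed while another person is at risk.

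**Working it through.** There is no figure to reproduce, because this is a check of procedure. The question is whether any text in the document takes a remote harm-to-others answer to staff.

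**Step 1. Set the survey-reported risks side by side.**

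| | Sexual assault | Suicidal ideation | Homicidal ideation or non-sexual threat to others |
|---|---|---|---|
| Collected by self-report | Yes (sections 6, 12.A) | Yes (sections 6, 12.A) | Yes, as risk of harm to others (section 12.A); no item named |
| Action tied to the disclosure | Staff and psychologist informed immediately (section 6) | Full risk assessment (section 6) | Immediate assessment promised (section 12.A) |
| Automatic survey alert | Listed | Listed | Not listed |

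The first two rows are filled for all three columns. Only the last row differs.

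**Step 2. Test each other provision that might supply the missing link.**

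- *Escalation to the psychologist (section 12.A).* It names homicidal ideation, but its starting condition is that staff are already concerned. It does not say how they come to know.
- *Immediate text and email alert (section 6, Protection Against Risks).* It applies when a question arises about mandated reporting law. Homicidal ideation towards a peer or an adult is not obviously such a question.
- *Threats to self or another person (section 6).* This concerns breaking confidentiality once a threat is known.
- *Contact with the family if other problems arise (section 6, Protection Against Risks).* This is a response, not a means of detection.
- *Contact within 24 hours (section 6, Protection Against Risks).* In context it follows from the two-trigger alert. Even if read as covering every teen, 24 hours is not immediate.
- *Reports to child protection and law enforcement for events involving risk of harm (section 12, Adverse Events).* This also presupposes that the event is known.
- *Weekly staff meetings (section 12).* These are too infrequent to deliver an immediate assessment.

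**Step 3. Combine.** Each provision either starts after staff know, concerns a different kind of disclosure, or works too slowly. None describes how a remote answer indicating homicidal ideation or a non-sexual threat reaches staff. The gap is that single step. What happens afterwards is written.

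**The case against.** The strongest reply is that silence in the protocol does not show that the trial lacks a route. The alert text does not call its list complete. The follow-up surveys, the suicide safety plan and the data and safety monitoring plan approved by the funder are separate documents, and item-level alert logic could sit in any of them. The promise of immediate assessment, triggered by the participant's own answer, arguably already obliges staff to see answers promptly. The provisions on threats, escalation and reporting show that harm to others was not overlooked.

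Much of this stands, and it limits what can be said. A reader might infer that harm-to-others answers go unread in this trial. The documents do not support that, since the survey programming is not among them. A reader might also infer that every form of harm to others lies outside the alert. That goes too far as well: the trigger refers to a reported sexual assault without limiting it to victimization, and perpetration is among the behaviors listed in section 10, so perpetration may already be covered. No harm-to-others item is named either, so it is unknown whether one exists that could carry an alert.

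What the reply does not remove is the mismatch inside the protocol. It writes an alert rule for all surveys, names two triggers, and elsewhere makes an equally firm promise about a risk that the rule omits. Someone programming the survey from this text would leave that risk out.

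**Conclusion.** The point holds in limited form. As written, the automatic alert does not cover homicidal ideation or non-sexual threats to others, although the plan foresees the former, says that risk of harm to others is measured by questionnaire, and commits to immediate assessment. The missing piece is the step from remote answer to staff, which arises at up to three follow-up surveys per participant and at any baseline done remotely.

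This rests on reading the two listed triggers as the rule to be programmed, and on the unseen survey programming and safety plan not already filling the gap. If they do, only the protocol text needs correcting. The number of remote surveys should not be read as a measure of risk: the documents give no rate of harm-to-others answers, so no count of affected answers or missed events can be derived. The point concerns participant and third-party safety. It does not bear on any outcome, analysis or feasibility criterion.

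**What to change.** In section 6 (Protection Against Risks), add homicidal ideation or intent to harm others as a trigger of the existing automatic notification in all surveys. State that an answer of this kind is handled under the immediate-assessment rule in section 12.A. Leave the sexual assault and suicidal ideation triggers, and the response times attached to them, as they are. The clinical response in section 12.A needs no change.

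First check the survey programming. If such an alert already runs, one sentence in the protocol is enough. Otherwise the cost is a minor protocol and IRB amendment, one more alert rule, and probably a few extra alerts for the on-call psychologist. If no existing harm-to-others item can carry the alert, one survey item would have to be added.
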